5.3.2 Secondary study parameters

The secondary safety and performance parameters will be compared between the two types of insulin using dependent t-tests or Wilcoxon signed rank tests. T-tests or Wilcoxon signed rank tests for:

- Time in hypoglycemia. It is hypothesized that the time below range is not higher for Lyumjev when compared to Humalog. A one tailed test shall be performed with:
 $H_0: \mu_{\text{Lyumjev}} \leq \mu_{\text{Humalog}}$
 $H_1: \mu_{\text{Lyumjev}} > \mu_{\text{Humalog}}$
- Time in euglycemia. It is hypothesized that the time in range is not lower for Lyumjev when compared to Humalog. A one tailed test shall be performed with

Revision	D02	Document number:	SAP
	Document title:	FAST-1	
	Status:	APPROVED	
	TPL 013.D02	This document is uncontrolled when printed	

$H_0: \mu_{\text{Lyumjev}} \geq \mu_{\text{Humalog}}$,

$H_1: \mu_{\text{Lyumjev}} < \mu_{\text{Humalog}}$

- Mean or median glucose. It is hypothesized that the mean or median glucose is not higher for Lyumjev when compared to Humalog. A one tailed test shall be performed with:

$H_0: \mu_{\text{Lyumjev}} \leq \mu_{\text{Humalog}}$

$H_1: \mu_{\text{Lyumjev}} > \mu_{\text{Humalog}}$

- Glycemic variability expressed as coefficient of variation and interquartile range. It is hypothesized that the glycemic variability is not higher for Lyumjev when compared to Humalog. A one tailed test shall be performed with:

$H_0: \mu_{\text{Lyumjev}} \leq \mu_{\text{Humalog}}$

$H_1: \mu_{\text{Lyumjev}} > \mu_{\text{Humalog}}$

The pharmacodynamic parameters and the main endpoint will be calculated for the whole study period and for daytime (06:00–00:00 h) and nighttime (00:00–06:00h) separately.

Other endpoints are the AP-related parameters:

- Daily administered dosage of glucagon;
- Daily administered dosage of insulin;
- The percentage of time that the closed loop algorithm is active.

No statistical testing will be performed on these parameters.

6 Missing data

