1. INTRODUCTION AND RATIONALE

Over the last decade insulin delivery and blood glucose monitoring have evolved, facilitating better glucose control for patients with type 1 diabetes mellitus. Continuous subcutaneous insulin infusion and glucose sensors combined with an insulin delivery algorithm constitute a closed loop system or artificial pancreas. A closed-loop system can be categorized as mono-hormonal (subcutaneous insulin administration) or bi-hormonal (subcutaneous insulin and glucagon administration).

Inreda Diabetic B.V. (Goor, the Netherlands) developed a bi-hormonal artificial pancreas (AP) to provide automated glycemic control for insulin treated adult patients. The AP consists of two subcutaneous glucose sensors to continuously measure glucose values and an algorithm to determine the amount of insulin (Humalog, Eli Lilly) or glucagon (GlucaGen[®], Novo Nordisk) to be administered.

The AP is CE-certified in February 2020. Different clinical studies (called APPEL 1 to 5: 'Algorithm to control Postprandial, Post exercise and night glucose Excursions in a portable closed loop format') were performed to test feasibility, safety and performance. These studies facilitated market approval. The APPEL 4 study showed comparable median glucose levels for closed loop and open loop (standard insulin pump) therapy, while the time in range (3.9–10 mmol/l) was higher for closed loop [1]. Improvements were made to the prototype to allow patients to operate the system independently. Hereafter, the device was tested for two weeks in order to include multiple replacements of disposables (glucose sensors, infusion sets, and insulin- and glucagon cartridges) and observe the self-learning glucose control algorithm adapting to the individual patient (APPEL 5 study) [2]. This study demonstrated that the bi-hormonal closed-loop system provides better glycemic control than standard open loop therapy. The median time in range was higher during closed-loop (86.6% [IQR 84.9-88.3]) compared to patients' usual diabetes care (53.9% [49.7-67.2], $p < .001$) Time below range (< 3.9 mmol/l) also significantly improved during closed-loop compared to usual diabetes care (0.4% [IQR 0.1-0.8] vs 2.0% [IQR 0.7-3.6]).

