10.2 Secondary study parameters

The pharmacodynamic parameters will be compared between Lyumjev insulin and Humalog insulin using a dependent t-test or Wilcoxon signed rank test for paired measurements (significance level of 0.05).

Pharmacodynamic parameters will be tested for the whole day, daytime and nighttime.

The AP-related parameters will be compared between Lyumjev insulin and Humalog insulin using a dependent t-test or Wilcoxon signed rank test for paired measurements (significance level of 0.05).

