5.3 Standard analysis

The distribution of each parameter (primary, secondary and other study parameters) will be assessed with a histogram and/or q-q plot. For the parameters that are being compared with dependent/paired tests, the distribution of the difference between the groups will be assessed. Based on these assessments, the decision for using data transformations and parametric or nonparametric descriptive analysis and statistical testing will be made for each (group of) parameter(s).

Subsequently, carry-over and period effects will be assessed because of the cross-over design of the study. For each parameter that will be compared between open loop and closed loop, the two randomization groups are first compared using two unpaired t-tests or Mann-Whitney U-tests:

- Sum of open loop and closed loop result (carry-over);
- Difference between the open loop and closed loop result (period).

If a significant difference is found in one of these tests, a carry-over/period effect is present. In that case, the results for that parameter of the second study period cannot be used for the analysis (to estimate the treatment effect) and paired testing will not be possible.

For all statistical tests described in this chapter, a p-value ≤ 0.05 is defined to indicate statistical significance. Descriptive analyses will be performed on the subjects presented in 5.3.3.

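### SAP 5.3.2 makes each secondary hypothesis of no worsening the null of a one-tailed harm test, with no margin or interval, so no planned test can support it

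*SAP*

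**What the plan says.** SAP 5.3.2 sets out four hypotheses:

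- Time in hypoglycemia: "It is hypothesized that the time below range is not higher for Lyumjev when compared to Humalog".
- Time in euglycemia: "It is hypothesized that the time in range is not lower for Lyumjev when compared to Humalog".
- Glucose level: "It is hypothesized that the mean or median glucose is not higher for Lyumjev when compared to Humalog".
- Variability, measured by coefficient of variation and by interquartile range: "It is hypothesized that the glycemic variability is not higher for Lyumjev when compared to Humalog".

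Each is followed by a one-tailed paired t-test or Wilcoxon signed rank test. For time in range, H0 is Lyumjev at or above Humalog and H1 is Lyumjev below. For the others, H0 is Lyumjev at or below Humalog and H1 is Lyumjev above. SAP 5.3 adds that a p-value of at most 0.05 "is defined to indicate statistical significance".

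SAP 5.3.1 treats the primary parameter the other way round: the hoped-for statement is H1, with a margin of 3.125%.

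Protocol section 2 asks for differences in pharmacodynamics to be assessed. Protocol 10.2 plans paired tests at 0.05 for these parameters, without a direction, and says "Pharmacodynamic parameters will be tested for the whole day, daytime and nighttime". SAP 5.3.2 says only that daytime and nighttime values will be calculated.

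Under SAP 8.1, deviation 3, closed-loop outcomes now come from 7 of the 12 participants, all in the Humalog-Lyumjev sequence.

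**The concern.** A significance test can give evidence for its alternative and never for its null. Here the statement that the SAP wants to examine is the null. The SAP names no margin that would turn it into a non-inferiority question, plans no interval that would show how much worsening the data exclude, and does not say how a non-significant result will be reported.

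The risk lies in the report. A reader who sees a hypothesis of not higher followed by p > 0.05 may take it as confirmed. Under that reading, fewer or noisier data make confirmation easier, and the analysis set has shrunk from 12 to 7. The parameters include time in hypoglycemia, and the protocol (summary, 6.4 and 11.4) names altered effectiveness leading to hypo- and hyperglycemia as the most prominent risk.

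**Working it through.** **1. What each planned test can conclude.** This needs no assumed numbers.

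| Result | What it shows | Supports the stated hypothesis? |
|---|---|---|
| p ≤ 0.05 | Lyumjev worse | No, contradicts it |
| p > 0.05, estimate towards harm | Inconclusive | No |
| p > 0.05, estimate towards benefit | Not significant by construction | No, the SAP defines no rule for it |

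**2. Number of tests.** The measures are time below range, time in range, mean or median glucose, coefficient of variation and interquartile range. That is 5 one-tailed tests stated in the SAP. Daytime and nighttime tests come from Protocol 10.2, which gives no direction.

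**3. The plan's own figure.** Protocol 4.4 and SAP section 3 give means 12.8 and 9.675, SD 3.3 in each period and correlation 0.70.

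- SD of the difference = 3.3 × √(2 × (1 − 0.70)) = 2.556.
- Standardised effect = 3.125 / 2.556 = 1.223.
- Noncentral t, two-sided 0.05: power 0.893 at n = 9 and 0.929 at n = 10. The stated 10 is reproduced.

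This sizing is for the primary comparison. The documents give no size, power or margin for the secondary hypotheses.

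**4. Illustration: non-significance under real harm.** Assume a true harm of 0.5 SD of the paired difference and no period effect. The effect size is mine. With df = n − 1 and noncentrality 0.5 × √n, the chance of non-significance is the noncentral t distribution function at the critical value. The two-sided column also counts rejection in the opposite tail.

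| n | Noncentrality | One-tailed critical t | Missed, one-tailed 0.05 | Missed, two-sided 0.05 |
|---|---|---|---|---|
| 12 | 1.732 | 1.796 | 50.8% | 65% |
| 10 | 1.581 | 1.833 | 57.3% | 71% |
| 7 | 1.323 | 1.943 | 68.1% | 80% |

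The last column matters for interpretation: a two-sided test misses the harm more often still. The miss rates reflect the sample size. They show why p > 0.05 is not evidence of not worse; they do not measure the effect of where H0 was placed.

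**5. Illustration: a uniform benefit.** If all 7 patients improved, an exact Wilcoxon test would give a harm-tail p of 1.0. The same data give 2/128 = 0.016 two-sided. The SAP names the Wilcoxon test without saying whether it is exact.

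**6. Width of an interval at n = 7** (6 df), in SDs of the paired difference.

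- 95% half-width: 2.447 / √7 = 0.92.
- 90% half-width: 1.943 / √7 = 0.73. This is also the threshold of the one-tailed 0.05 t-test, so a 90% t interval agrees with that test. With a 95% interval, an observed harm between 0.73 and 0.92 SD is significant on the harm test while the interval includes zero.

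**The case against.** The strongest reply is that one-tailed harm tests are legitimate safety screens, that these are secondary parameters for which the trial was not sized, and that the SAP nowhere says non-significance will be read as proof. All of that stands. Leaving superiority untested on secondary parameters is also a permissible choice. None of it supplies a test of the hypotheses the SAP states. Nor can the word *hypothesized* be taken to mean the null, because SAP 5.3.1 uses it for H1.

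Four stronger readings are tempting, and the documents do not support them:

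- *Fifteen one-tailed tests (5 measures × 3 windows).* This joins the SAP's direction to the protocol's windows. SAP 5.3.2 only calculates the daytime and nighttime values, and Protocol 10.2 tests them without a direction. The two documents differ, and that should be stated.
- *No planned result of any kind can bear on the hypotheses.* SAP 5.3 also plans descriptive analyses, which may lean one way. The limit applies to the planned tests.
- *The sponsor will claim, or has claimed, that Lyumjev is not worse.* Neither document says so, and the clinical investigation report is not among them.
- *The 51% to 68% miss rates measure the fault.* They come from small samples, as the two-sided column shows.

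**Conclusion.** The point holds and should be fixed. For all four stated hypotheses, covering five measures, the planned one-tailed test cannot support the hypothesis it accompanies, and under the SAP a benefit on these measures cannot reach significance. This follows from the text alone and would be equally true in a large trial. The primary comparison does not share the fault, since its H1 points towards benefit.

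The illustrative figures rest on an assumed harm of 0.5 SD, approximately normal paired differences and no period effect. The last cannot be checked in the data now used: SAP 5.3 says that "the two randomization groups are first compared using two unpaired t-tests or Mann-Whitney U-tests" for carry-over and period effects, and only one sequence remains in the closed-loop analysis.

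**What to change.** Keep the pre-specified text of SAP 5.3.2. Add one entry to SAP section 8, repeated in the clinical investigation report and marked post hoc as Protocol section 10 requires. It should say that:

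1. The paired differences (Lyumjev minus Humalog) for the 5.3.2 parameters are reported with two-sided confidence intervals, labelled descriptive and post hoc.
2. The one-tailed p-values test for harm only, and a non-significant result does not show that Lyumjev is not higher, or not lower, than Humalog.
3. No claim of not worse is made without a margin, and any margin set now is labelled post hoc.
4. The interval level is stated together with its relation to the one-tailed 0.05 test. A 90% t interval matches the t-test. If 95% is used, a significant harm test is still reported when the interval includes zero.
5. An interval that excludes zero on the side of benefit is not a confirmatory claim.
6. The SAP's one-tailed tests and the protocol's undirected tests, including those by daytime and nighttime, differ.
7. Closed-loop data come from one sequence (n = 7), so treatment and period cannot be separated.

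The cost is one deviation entry, an interval column in the tables and a short statement in the report; no new data are needed. The downsides are that the change comes after the data were analysed, that the intervals will be wide (95% half-width about 0.92 SD of the difference at n = 7), and that without a margin the stated hypotheses remain formally untested.

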2. OBJECTIVES

Primary Objective:

The primary objective is to determine the efficacy of Lyumjev in the AP. Main parameter to express efficacy is the time above range (>10 mmol/l). It is hypothesized that the time above range is lower using Lyumjev compared to the standard use of care: Humalog.

Secondary Objectives:

Secondary objectives are:

- to assess safety parameters;
- to assess differences in pharmacodynamics between Lyumjev and Humalog;
- to assess differences in AP-related outcomes between Lyumjev and Humalog.

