8.1.2 Secondary study parameters/endpoints (if applicable)

The safety parameters are:

- Side effects of Lyumjev

The pharmacodynamic parameters are:

- Proportion of time spent in euglycemia (3.9-10.0 mmol/l);
- Proportion of time spent in hypoglycemia (<3.9 mmol/l);
- Proportion of time spent in level 2 hypoglycemia (<3.0 mmol/l);
- Proportion of time spent in level 2 hyperglycemia (>13.9 mmol/l);
- Mean/median glucose value;
- Glycemic variability expressed as coefficient of variation and interquartile range (IQR).

The pharmacodynamic parameters and the main endpoint will be calculated for the whole study period and for daytime (06:00–00:00 h) and nighttime (00:00–06:00 h) separately.

AP-related parameters are:

- Daily administered dosage of glucagon;
- Daily administered dosage of insulin;
- The percentage of time that the closed loop algorithm is active.

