8.1 Description of the deviations from the SAP

1. Standard deviation (SD) of the glucose value

- a. Rationale: SD of the glucose value was included as variable because of its added value to indicate glycemic variability.
- b. Detailed description: the SD of the glucose value was added as parameter considering it is a commonly used parameter besides the coefficient of variation and interquartile range of the glucose value to indicate glycemic variability. The SD was calculated for day time, night time and the combination. No data were affected by the addition of this parameter.
- c. Date of decision: May 1, 2023.
- d. People involved in the decision (with signature): [name], [name] and [name].

2. Time below range (TBR) and time above range (TAR)

- a. Rationale: level 1 and level 2 for the TBR and TAR were included in order to report all the important glycemic metrics, following the International Consensus guidelines.
- b. Detailed description: according to the SAP, only the TBR and TAR in total should be calculated (not as separate levels). In addition to the total TBR and TAR, also level 1 and 2 of the TBR and TAR were calculated. These are essential parameters to indicate glycemic control, following the International guidelines on how to report glycemic metrics (Battelino *et al*, Lancet Diabetes Endocrinol (2023)). These metrics were calculated for day time, night time and the combination. These additional parameters had no effect on the data.

Revision	D02	Document number:	SAP
	Document title:	FAST-1	
	Status:	APPROVED	
	TPL 013.D02	This document is uncontrolled when printed	

- c. Date of decision: May 1, 2023.
- d. People involved in decision (with signature): [name], [name] and [name].

3. Exclusion of AP data acquired for five participants

a. Rationale:

A critical procedural error was discovered in the process of data analysis, which led to invalidity of a part of the FCL data. FCL data from the Lyumjev-Humalog sequence (n=5) had to be excluded. Other data from this sequence could still be included (e.g., adverse events). To mention that all FCL data from the Humalog-Lyumjev sequence (n=7) were included.

b. Details on deviation:

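### SAP 5.3.2 drops, without explanation, paired comparisons that protocol 10.2 plans for the AP-related and level 2 glucose metrics, and deviation 2 then logs the level 2 metrics as new

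*SAP*

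**What the plan says.** **AP-related parameters.** The third secondary objective in protocol section 2 is "to assess differences in AP-related outcomes between Lyumjev and Humalog". Protocol 8.1.2 places daily glucagon, daily insulin and the percentage of time in closed loop among the secondary parameters. Protocol 10.2 gives the analysis: "The AP-related parameters will be compared between Lyumjev insulin and Humalog insulin using a dependent t-test or Wilcoxon signed rank test for paired measurements", at a significance level of 0.05. SAP 5.3.2 reclassifies them ("Other endpoints are the AP-related parameters") and closes with "No statistical testing will be performed on these parameters".

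**Level 2 glucose metrics.** Among the pharmacodynamic parameters, protocol 8.1.2 lists "Proportion of time spent in level 2 hypoglycemia (<3.0 mmol/l" and "Proportion of time spent in level 2 hyperglycemia (>13.9 mmol/l". Protocol 10.2 applies paired tests to the pharmacodynamic parameters as a group, for the whole day, daytime and nighttime. The tests named in SAP 5.3.2 cover time in hypoglycemia, time in euglycemia, mean or median glucose, coefficient of variation and interquartile range. Neither level 2 metric is there.

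**Deviation log.** Deviation 2 in SAP 8.1, decided on 1 May 2023, says "according to the SAP, only the TBR and TAR in total should be calculated". It records levels 1 and 2 as extra calculations prompted by an international consensus guideline. It does not mention that protocol 8.1.2 already contained level 2.

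**The concern.** The protocol leaves specific details to the SAP, but removing a planned comparison is more than a detail, and the SAP gives no reason for it.

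Three things are at stake:

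- The AP objective loses the formal comparison planned for it. The device delivers both insulin and glucagon, so a change in time above range is hard to interpret without the accompanying change in hormone use and its uncertainty.
- The level 2 metrics describe the more extreme excursions. The protocol itself names altered effectiveness leading to hypo- and hyperglycemia as the most prominent risk.
- Protocol section 10 requires SAP deviations to be reported as decided after preliminary data evaluation and therefore post-hoc. Applied to deviation 2, that rule would put a post-hoc label on metrics fixed in the protocol.

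**Working it through.** **1. Planned tests side by side** (protocol 8.1.2 and 10.2 against SAP 5.3.2)

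| Secondary metric | Protocol: paired test | SAP: test |
|---|---|---|
| Time 3.9-10.0 mmol/l | yes, 3 windows | yes |
| Time <3.9 mmol/l | yes, 3 windows | yes |
| Time <3.0 mmol/l | yes, 3 windows | not listed |
| Time >13.9 mmol/l | yes, 3 windows | not listed |
| Mean/median glucose | yes, 3 windows | yes |
| Coefficient of variation | yes, 3 windows | yes |
| Interquartile range | yes, 3 windows | yes |
| Daily glucagon | yes | excluded |
| Daily insulin | yes | excluded |
| Closed-loop time | yes | excluded |

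Metrics: 7 + 3 = 10 in the protocol, 5 in the SAP, 5 missing. Tests: 7 × 3 + 3 = 24 in the protocol; 5 × 3 = 15 in the SAP if it tests every window; missing 3 + 2 × 3 = 9. The SAP says only that the windows are calculated. If it tests the whole day alone, it has 5 tests. That is a separate ambiguity and is not counted here.

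**2. Could the SAP's later reference to pharmacodynamic parameters include level 2?** Read alone, that sentence in 5.3.2 might. Deviation 2 closes the question by saying that separate levels were not planned. It also reports level 2 as calculated, not tested, so it does not restore the protocol's test.

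**3. Daily-average formula** (SAP section 6). The numerator is a 25-day sum and the denominator is 30 − X. If X counts missing days within the 25 analysed days, the correct denominator is 25 − X, and the result is (25 − X)/(30 − X) of the true daily mean:

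- X = 0: 25/30 = 0.833
- X = 5: 20/25 = 0.80

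Equal X in both periods shrinks an absolute difference by that factor. Unequal X creates a difference where there is none: 0.80/0.833 = 0.96, or 4%, for X = 5 against X = 0. The formula is right only if the five training days are counted in X (25/25 = 1 with nothing missing), which the text does not say.

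**4. Precision.** The plan's own figure first: SD of the difference = 3.3 × √(2 × (1 − 0.70)) = 2.556; standardised effect = (12.8 − 9.675)/2.556 = 1.2225. A two-sided paired t-test at 0.05 has power 0.893 with 9 subjects and 0.929 with 10, which reproduces the stated 10. Solving the same power function for the effect detectable with 80% power gives 0.89 SD at n = 12, 1.00 SD at n = 10 and 1.27 SD at n = 7. Seven is the number with usable AP data after deviation 3.

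**5. Confounding.** All seven took Humalog first and Lyumjev second. For them, Lyumjev minus Humalog is the same quantity as period 2 minus period 1, and no analysis of these seven alone can separate the two.

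**6. Multiplicity, for scale only.** With independent tests at 0.05, the chance of at least one false positive is 1 − 0.95^15 = 0.54 for 15 tests and 1 − 0.95^24 = 0.71 for 24. The metrics are correlated, so the true figures differ. Neither document describes an adjustment.

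**The case against.** The strongest reply is that little of substance is lost, and several stronger readings do fail.

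- **The AP objective has no comparison at all.** A reader might infer this, but 5.3.2 removes testing only. SAP 5.3 plans descriptive analysis for all parameters, and section 6 defines per-period daily averages and percentage of time active. The objective speaks of assessing differences, not of a hypothesis test. What is missing is the formal comparison that protocol 10.2 planned.
- **It is the only objective without a test.** Neither document plans a between-insulin test of side effects, so the safety objective has none either. The AP objective is the one that lost a planned test.
- **Level 2 has lost its pre-specified status.** The protocol still lists it, and deviation 2 had it calculated. The SAP never uses the word post-hoc; that label follows from the protocol's rule on deviations. The error lies in how the log describes the metrics.
- **A designated safety endpoint was dropped.** Protocol 8.1.2 classes level 2 hypoglycemia as pharmacodynamic. Its only listed safety parameter is side effects, although SAP 5.3.2 uses the looser heading of safety and performance.
- **The tests were removed after seeing the data.** The revision history says D02 added only deviations and signatures. The no-testing sentence therefore dates from D01 (29-08-2022), before the May 2023 decisions.

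It is also fair that a test of time below 3.0 mmol/l would have little to work with. Protocol section 1 gives a closed-loop median of 0.4% for all time below 3.9 mmol/l in the earlier two-week study, about 0.004 × 1440 = 5.8 minutes a day, and time below 3.0 is a subset of that. Total time below 3.9 is still tested. This favours intervals over bare p-values, but it does not explain an undocumented departure from the protocol.

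**Conclusion.** The mismatch is real, stands in current text and is unexplained. Five of ten protocol-tested secondary metrics (9 of 24 tests, if the SAP tests every window) have no planned test in the SAP. Objective 3 has descriptive values but no formal comparison. Deviation 2 presents two protocol-specified metrics as additions, although only its level 1 split is new.

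There is one knock-on effect. The protocol wants carry-over and period effects assessed for all parameters, whereas SAP 5.3 checks only those being compared, so the dropped comparisons lose that check too. For the AP data this no longer has practical force, because the check compares two sequences and only one remains.

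The consequence is moderate: secondary, supportive results and the accuracy of the deviation record. The counts treat mean/median glucose as one metric and coefficient of variation and interquartile range as two. The 0.83 factor assumes that X is counted within the 25 analysed days.

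**What to change.** Enter a dated, logged correction in SAP section 8 stating that it restores the protocol's analysis. Do not rewrite 5.3.2 silently: the analysis decisions were taken in May 2023, and a rewrite now would make these tests look as if the SAP had always planned them. The correction should:

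1. Put the daily-average formula on one basis, with numerator and denominator covering the same 25 days and X counted within them, before any doses are compared.
2. Report the paired difference with a 95% confidence interval, together with the protocol's paired test, for daily insulin, daily glucagon, closed-loop time, time <3.0 mmol/l and time >13.9 mmol/l, the last two in the three windows.
3. Reword deviation 2 to say that level 2 was pre-specified in protocol 8.1.2 and omitted from the SAP, and that only the level 1 split is new.
4. Label these comparisons exploratory and confounded with period, since they rest on 7 participants in the Humalog-Lyumjev sequence.

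The data are already collected. The cost is the wording and up to 9 further supportive comparisons (3 AP-related, plus 2 metrics in 3 windows) with no multiplicity adjustment, so the intervals should carry the interpretation.
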